the frames of the patients' existing glasses (or on a mock frame if the patient does not wear glasses) in order to measure head pitch, roll and yaw. The subjects will be asked to walk around a long empty corridor during which time they will be timed and videotaped and IMU data will be acquired. Then, participants will be asked to walk the same corridor after obstacles are arranged in the corridor every 1-2 meters. Obstacles will be short pieces of foam lying on the floor, knee to waist high cardboard boxes, or pieces of foam hanging from the ceiling. A research assistant will follow close to participants in order to provide assistance should this be required. Testing mobility in the presence of obstacles is important in order to more closely approximate real-world scenarios. Video recording is essential in order to correlate aberrancies in IMU data with obstacles in the patients' environment. The same procedure will be repeated with the patients wearing optical head-mounted display technology after the period of in-home adaptation to the technology with the device turned off (to serve as a negative control) and with the device turned on.

To accomplish Aim 3:

Participants will all complete the Impact of Vision Impairment and Independent Mobility Questionnaire at the time of their enrollment in the study. These surveys will be completed again after the period of in-home adaptation to the OHMD. We will also analyze qualitative data collected through open-ended interviews after use of HMD.

We will conduct statistical analyses, as detailed in Section 2e, to describe associations between outcomes assessed throughout our Aims.

b. Eligibility

Participants with retinal dystrophy will be recruited into this study from the Retinal Dystrophy Clinic in the Department of Ophthalmology and Visual Sciences at the University of Michigan.

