Normal controls will be included to adjust for the baseline impact of HMD on visual fields and gait parameters and to compare these to data from patients with RP. Comparing to a group of age-matched control patients will allow us to investigate and understand the true impact of HMD on visual fields, gait, and quality of life. Control participants will be recruited from the Comprehensive and Pediatric Ophthalmology Services at the University of Michigan. We will seek to enroll up to 40 subjects in order to obtain ten patients and ten age-matched controls with complete data, allowing room for those who don't complete both study visits and technical errors with equipment.

Criteria

Inclusion criteria for subjects with retinal dystrophy:

- diagnosis of retinal dystrophy
- severe vision loss that constitutes legal blindness
- able to perform a reliable Goldmann visual field test
- constricted visual field less than or equal to 20 degrees by Goldmann perimetry using the III4e stimulus in at least one eye with best-corrected visual acuity $\geq 20/60$

Inclusion criteria for control subjects:

- healthy controls
- able to perform a reliable Goldmann visual field test

Exclusion criteria for subjects with retinal dystrophy:

- movement disorder that precludes evaluation of mobility
- functional vision loss
- pregnant women

Exclusion criteria for control subjects:

- visually significant ocular condition other than correctable refractive error
- movement disorder that precludes evaluation of mobility
- functional vision loss
- pregnant women

c. Study Setting

Patients will be recruited from the Retinal Dystrophy Clinic of the Department of Ophthalmology and Visual Sciences at the University of Michigan; controls will be recruited from the Comprehensive and Pediatric Clinics of the Department of Ophthalmology and Visual Sciences at the University of Michigan. Study exams, clinical testing, surveys and interviews will be completed in the Kellogg Clinical Research Center. Mobility testing will be conducted in a hallway located in the Kellogg Clinical Research Center.

d. Outcome measures

Primary Outcome Measures:

- Change in the planimetric area of Goldmann visual field with the use of head-mounted display technology compared to baseline (measured in degrees squared):
Using computer software we will calculate the area of participants' Goldmann visual fields in order to obtain a summary quantitative measurement of the extent of peripheral vision.

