Secondary Outcome Measures:

- Change in gait speed compared to baseline (measured in seconds):
Gait speed will be measured using an inertial measurement unit attached to participants' shoes and will quantify the time taken to move from the beginning to end of a short mobility course.

Other Outcome Measures:

- Change in patient-reported ability for independent mobility as assessed by subject responses a validated questionnaire:
Independent Mobility Questionnaire (scored from 35 to 175 with 175 representing extreme mobility impairment)
- Change in patient-reported mobility and independence as assessed by subject responses a validated questionnaire:
Mobility and Independence domain of the Impact of Vision Impairment Questionnaire (scored from 0 to 33 with 0 representing poor mobility and independence)
- Change in stride length compared to baseline (measured in mm):

Inertial measurement units attached to participants' shoes will track the length of each step as they walk through a short mobility course.

- Change in stride width compared to baseline (measured in mm):
Inertial measurement units attached to participants' shoes will track the width of each step as they walk through a short mobility course.
- Change in foot orientation compared to baseline (measured in degrees):
Inertial measurement units attached to participants' shoes will track the orientation of their feet as they walk through a short mobility course.

e. Planned Data Analysis

To address Aim 1 the visual field will be assessed before and after being trained to use optical head-mounted display technology. The Goldmann visual field plots will be scanned and the planimetric areas for each stimulus size will be measured using Adobe Photoshop CC (San Jose, CA) as previously described (8). In brief, using a scale of 10 degrees on the visual field, the corresponding number of pixels are determined, and the units are set to millimeters. Areas are measured in mm² using the Magic Wand tool and are converted to degrees squared. Areas of scotomas are subtracted from the total area. We will analyze the change in area before and after a 2-4 week period of adaptation to the OHMD. The adaptation period is important as it will allow subjects to become familiar with how to use the device and to gain insight into how using such a device may impact their life. The Mann-Whitney U test will be used to compare change in visual field area between patients and controls.

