To address Aim 2 we will measure change in gait speed with and without the use of OHMD. We will calculate percent preferred walking speed to compare the ratio of gait speed measured in the presence and absence of physical obstacles. We will also use our data processing algorithms to reconstruct the paths of the feet and head movements during the planned experiments from which we can estimate mobility parameters (9–11). For gait, we will gather measures of stride length, width and period, and their variabilities, from straight-line walking, lateral/foot-angle relation, stride frequency, ground contact time, etc. For head movement we will gather measures of head pitch, head roll and head yaw. The mean and standard deviation of each gait and head movement parameter will be compared before and after being trained to use optical head-mounted display technology (11,12). We will use Wilcoxon signed-rank test to test for significant differences. Significant changes (and trends) will be assessed for direction and magnitude, and resulting values will be compared to gait and head movement parameter norms before and after using the optical head mounted display. The Mann-Whitney U test will be used to compare changes in gait parameters between patients and controls.

To address Aim 3 we will use the Wilcoxon signed-rank test to determine whether individual participants' survey scores changed from baseline when using optical head mounted display technology. We will also use the Mann Whitney U test to compare changes in survey scores between patients and controls. Cohen's d will be calculated to measure the overall effect size of the intervention as measured by the surveys. Minimum clinically important differences will also be calculated (ratio of change in visual ability to 1.95 standard errors of the measured change) to determine if changes in each individual's visual ability were clinically important.

We will also calculate Spearman correlations between variables (visual field area, mobility parameters and survey results) and use multiple regression to investigate associations while controlling for covariates.

Image 1. The Epson Moverio® Head Mounted Display.

Image 2. The Actigraph Link Inertial Motion Unit.

References

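### The Aim 3 rule for individual survey change tests whether a change exceeds measurement error, so it can support a label of detectable change but not of clinical importance

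*Combined protocol and SAP*

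**What the plan says.** Section e analyses the Aim 3 surveys at two levels.

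- **Group level.** The Wilcoxon signed-rank test is given the purpose "to determine whether individual participants' survey scores changed from baseline". A Mann-Whitney test compares the changes of patients and controls, and Cohen's d summarises the overall effect.
- **Individual level.** The plan then adds: "Minimum clinically important differences will also be calculated (ratio of change in visual ability to 1.95 standard errors of the measured change". Its stated purpose is "to determine if changes in each individual's visual ability were clinically important". No cut-off for the ratio is printed; an absolute value of 1 is the natural one.

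Under Aim 3 in section a, participants "complete the Impact of Vision Impairment and Independent Mobility Questionnaire at the time of their enrollment in the study". The plan continues: "These surveys will be completed again after the period of in-home adaptation to the OHMD". Section d lists both surveys among the Other outcome measures and gives their ranges: "Independent Mobility Questionnaire (scored from 35 to 175 with 175 representing extreme mobility impairment" and, for the mobility domain of the vision impairment questionnaire, "scored from 0 to 33 with 0 representing poor mobility and independence". For neither instrument do the documents give a standard deviation, a reliability, a standard error or a number of points that would count as important. An open-ended interview follows device use, but section e does not link it to the rule.

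**The concern.** Whether a change can be told apart from measurement error and whether it matters to the participant are different questions. The first depends on how precisely the questionnaire measures. The second needs outside information, such as a patient rating of change or an established threshold in points. The plan takes a calculation that addresses the first and uses it to decide the second.

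At stake is a sentence that a report of this pilot could well contain: that so many of the patients had a clinically important improvement with the device. Section b plans "in order to obtain ten patients and ten age-matched controls with complete data", so such a count would rest on about ten people per group and could be read as evidence of benefit. Followed exactly, the plan would produce that sentence, and its counterpart about people without important change, from a calculation that contains no information on importance.

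**Working it through.** **Inputs.** The multiplier 1.95 is from section e. The cut-off of 1 on the absolute ratio, and the reading of the standard error as one person's error of change, are inferred from the wording about each individual. Reliability (0.80, 0.90, 0.95) and between-person SD (15 to 30 points on the 35-175 scale, 5 to 8 points on the 0-33 scale) are not in the documents. They are assumptions, shown as ranges.

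**Step 1: what the multiplier implies.** The plan has no derived figure to reproduce here, so the multiplier is converted to an error rate. A person is flagged when |change| ≥ 1.95 × SE of change. With no true change and normal errors the probability is 2 × (1 − Φ(1.95)) = 2 × 0.0256 = 0.0512. An exact 5% test would use 1.96; the difference is immaterial.

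**Step 2: what enters the rule.** Two quantities enter: the change and its standard error. Neither carries a value judgement, an anchor or a threshold in points.

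**Step 3: what moves the cut-off.** With SE of change = SD × √(2(1 − r)), the cut-off is 1.95 × SD × √(2(1 − r)).

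| Assumed reliability r | √(2(1 − r)) | Cut-off in SD | Points on 35-175 scale, SD 15 to 30 | Points on 0-33 scale, SD 5 to 8 |
|---|---|---|---|---|
| 0.80 | 0.632 | 1.23 | 18.5 to 37.0 | 6.2 to 9.9 |
| 0.90 | 0.447 | 0.87 | 13.1 to 26.2 | 4.4 to 7.0 |
| 0.95 | 0.316 | 0.62 | 9.2 to 18.5 | 3.1 to 4.9 |

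The cut-off halves across the range (1.233 / 0.617 = 2.0) with no change in what patients experience. For example, an observed change of 0.80 SD gives a ratio of 0.80/1.233 = 0.65, 0.80/0.872 = 0.92 or 0.80/0.617 = 1.30. It is not flagged in the first two cases and is flagged in the third. Only the assumed precision differs.

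**Step 4: the other reading of the standard error.** If it meant the standard error of the mean change in ten patients, the cut-off would be 1.95/√10 = 0.617 SD of change. With zero mean change and normal changes, 2 × (1 − Φ(0.617)) = 0.54 of individuals would exceed it. That reading fits the individual purpose poorly, and it gives no measure of importance either.

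**The case against.** The strongest reply is that this is a dispute about a label. The formula stands next to the label, so a reader can see that the rule is distribution-based, and such thresholds can be defended as proxies for importance. Relabelling changes no number. The rule is not a listed outcome, and it supplements exploratory outcomes of a pilot. The point about limited impact stands. The proxy argument does not rescue the text: the plan neither calls the ratio a proxy nor justifies it as one, and says that it will settle whether each change was important.

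A reader might draw four stronger conclusions that the documents do not support.

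- **That flag rates show harm from the wording.** With no true change, the chance that at least one of ten patients is flagged on one survey is 1 − (1 − 0.0512)^10 = 41% in either direction, or 1 − (1 − 0.0256)^10 = 23% for improvement only. These are properties of the ratio and apply unchanged once it is called detectable change. They are not evidence for the fix.
- **That the rule readily labels trivial changes important.** Over reliability 0.80 to 0.95 a true change of 0.2 SD would be flagged in its own direction in only about 5% to 9% of people. The objection is that importance is not measured, not that the threshold is lax.
- **That the plan poses a separate individual question which the ratio was meant to answer.** The phrase "to determine whether individual participants' survey scores changed from baseline" is the purpose given to the Wilcoxon test, not an open question left for the ratio.
- **That the unstated sign convention and source of the standard error are errors.** Section d says what one end of each scale means, so the direction of improvement can be inferred. The source of the standard error is a drafting detail. Neither is part of this point.

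The wording on visual ability may also mean person measures with their own standard errors rather than raw scores. The table does not model that case, but the conclusion is the same because the ratio is still change over error.

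**Conclusion.** The point holds for the mislabelled rule and no further. Read at the individual level with a cut-off of 1, the ratio is about a two-sided 5% test (0.051 under normal errors) of whether a person's change exceeds measurement error. A flagged change is detectable, not shown to be important; an unflagged change is not shown to be unimportant. That conclusion needs no assumed reliability or SD. The assumed values only illustrate that the cut-off follows precision, from 1.23 down to 0.62 between-person SD.

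The consequence is confined to the individual-level reading of the Aim 3 survey outcomes in a pilot. The visual field primary outcome, the sample size, the Wilcoxon and Mann-Whitney tests and Cohen's d are unaffected. The wording should be corrected before analysis, but it does not threaten the trial.

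**What to change.** In the Aim 3 part of section e:

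- Keep the ratio, computed with the individual standard error of change, and name it reliable (detectable) change, present when its absolute value is at least 1.
- Remove the statement that it determines clinical importance. Call a change clinically important only if an externally anchored threshold for that questionnaire is named before analysis. Otherwise report each person's change with its confidence interval.

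This costs a change of wording and no new visits or participant data. What is lost is the individual-level importance claim if no anchored threshold can be found, and the documents show none.

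There is also a practical cost, which exists under either label. An individual standard error needs item calibrations or a reliability, possibly from outside the sample, because section a has one administration before device use and one after and so gives no test-retest estimate. An internal estimate from ten patients would be imprecise: a sample alpha of 0.90 with 35 items (assumed from the 35-175 range) has a 95% interval of about 0.78 to 0.97, which puts the cut-off anywhere from 1.28 to 0.48 SD.
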